Low-dose ketamine infusions for
perioperative pain management in
patients undergoing laparoscopic gastric
bypass

NCT03448068

November 12, 2019

**Low-dose ketamine infusions for perioperative pain management in patients
undergoing laparoscopic gastric bypass**

PI: [name].

Sub-I(s): [name].

Statistician: [name]

IRB#: 17-000301

Initial Version:	09Dec2016
Revised:	15Feb2017 V2
Revised:	28Mar2018 V3
Revised:	12Nov2019 V4

Introduction

This document is a protocol for a human research study. This study will be carried out in accordance with the applicable United States government regulations and Mayo Clinic research policies and procedures.

Background

Obesity has become a public health crisis in the developed world, especially in the United States. According to the CDC, more than one-third (36.5%) of adults in the United States are obese as defined by a BMI greater than or equal to 30. A 2013 study estimated that 6.6% of the US population is morbidly obese (BMI > 40) (Sturm) Negative health consequences of obesity include cardiovascular disease, obstructive sleep apnea (OSA), systemic hypertension, pulmonary hypertension, diabetes, musculoskeletal problems and various malignancies (Adams BJA 2000). Given the severe health consequences of obesity and the difficulty that many patients have maintaining a healthy weight, surgical management of obesity has become an effective therapeutic option for many patients with morbid obesity (Elder Gastroenterology 2007).

The Roux-en-Y gastric bypass is considered the “gold standard” for weight loss surgery and it is frequently performed laparoscopically. It involves anastomosing the proximal portion of the stomach to the jejunum, bypassing most of the stomach and duodenum and restricting food intake (Ogunnaike A&A2002). Despite the efficacy and overall safety of weight reduction surgery, obese patients pose significant challenges for perioperative physicians and are at higher risk for adverse events postoperatively, especially pulmonary complications (Adams BJA 2000).

Obese patients have increased oxygen consumption, increased CO₂ production, reduced lung FRC and reduced chest wall compliance all of which puts them at risk for hypoxemia and hypercarbia particularly in the postoperative period (Adams BJA 2000). Opioids and other central nervous system depressants commonly administered perioperatively may potentiate these gas exchange problems and increase risk for adverse event.

Most concerning, however, is the association between obesity and obstructive sleep apnea (OSA) which is a risk factor for perioperative respiratory depression as well as respiratory arrest and death (Chung A&A2008, also multiple case reports). Up to 70% of patients undergoing bariatric surgery have OSA (Frey Obes Surg 2003). OSA is a disorder characterized by reduced tone in the upper airway muscles during sleep which causes periodic airway obstruction with subsequent apnea and oxygen desaturation. Obese patients are at particular risk of developing OSA at least in part due to fat deposits in the pharyngeal walls leading to reduced airway diameter (Romero Chest 2010). In addition, as discussed above, obese patients are more vulnerable to disordered gas exchange and have less reserve for tolerating brief periods of obstruction.

OSA patients are especially vulnerable to apneic events postoperatively due to surgical stress, the residual effects of anesthesia, disruption of the normal sleep cycle and

exposure to central nervous system depressants (Benumof Curr Op Anesth 2004). Opioids in particular are problematic as they cause respiratory depression and have been shown to depress the muscle tone of the upper airway (Craven 2007, White J Physiol 2009). However, poorly managed abdominal pain may itself compromise respiratory effort resulting in hypoventilation. Clinicians are often confronted with the challenge of balancing the risks of opioid therapy versus the respiratory consequences suboptimal pain control. Non-opioid analgesics such as acetaminophen and NSAIDs can be helpful and have little effect on the respiratory system or OSA (Chung). Other drugs such as dexmedetomidine and gabapentin have also shown promise for reducing perioperative opioids, though both drugs are also central nervous system depressants and it is unknown what effect they may have on airway muscle tone during sleep (Chung).

Ketamine is an NMDA antagonist that, at high doses (>1mg/kg), induces dissociative anesthesia with minimal effects on ventilation and airway reflexes (Gorlin). Low dose ketamine infusions (<0.3mg/kg/hour) have proven efficacy for reducing pain scores as well as reducing post-operative opioid consumption in a wide variety of surgical procedures (Gorlin JAnesthClinPharm 2016). Furthermore, even at anesthetic doses, ketamine has no negative effect on pharyngeal muscle tone (Drummond BJA 1996). For these reasons, low dose ketamine may be an ideal analgesic adjunct for patients undergoing gastric bypass. Sollazzi et al demonstrated lower PACU pain scores and opioid consumption in patients undergoing gastric bypass who received a combined ketamine/clonidine infusion in the operating room (Sollazzi SurgObesRelDis2009). However, to our knowledge, there have been no studies looking at combined intraoperative and postoperative ketamine infusions for gastric bypass.

Our hypothesis states that in laparoscopic gastric bypass patients intraoperative ketamine infusion combined with continuation for twenty-four hours post-surgery provides superior pain control and decreases post-operative opioid use versus standard non-ketamine therapy.

Study Objectives

Primary Objective

- To assess the efficacy of a standardized bolus and infusion dose of intravenous ketamine on perioperative opioid requirements in gastric bypass surgical patients.

Secondary Objective

- To assess the efficacy of a standardized bolus and infusion dose of intravenous ketamine on perioperative pain scores, patient satisfaction with pain management, and length of stay in hospital in gastric bypass surgical patients. To assess the safety and tolerability of intravenous ketamine by examining presence of post-operative nausea and vomiting, pruritus, sedation, agitation, hallucinations, delirium, and adverse respiratory events.

Study Design and General Description

- **Randomization after consent is obtained to either ketamine or standard therapy**

- **Standard therapy group study protocol**
 - Calculation of ideal body weight (IBW) – see calculator
 - Pre-operative dexamethasone 4mg IV
 - Pre-operative midazolam 1-2mg IV for anxiolysis at discretion of anesthesiologist
 - Induction of anesthesia
 - Propofol 2-3mg/kg IV (IBW) at discretion of anesthesiologist
 - Fentanyl 1mcg/kg IV (IBW)
 - Neuromuscular blockade with succinylcholine and/or rocuronium at the discretion of the anesthesiologist
 - Orotracheal intubation
 - Maintenance of anesthesia
 - Sevoflurane/rocuronium
 - Additional doses of fentanyl 0.5-1mcg/kg (IBW) at discretion of anesthesiologist
 - Emergence from anesthesia
 - Acetaminophen 1g IV unless contraindicated
 - Ketorolac 30mg IV unless contraindicated
 - Ondansetron 4mg IV unless contraindicated
 - Suggamedex 2mg/kg or 4mg/kg dose (Actual BW) depending on twitch response per drug manufacturer's recommended protocol
 - Post-operative analgesia
 - Hydromorphone PCA 0.2mg/8 min
 - Acetaminophen 1g IV Q8 ATC x 3 additional doses
 - Ketorolac 15mg IV Q6 ATC x 3 additional doses
 - Other post-operative care as per usual surgical routine

- **Ketamine therapy group**
 - Ketamine 0.3mg/kg (IBW) bolus with induction
 - Ketamine infusion 0.2mg/kg/hr. (IBW) initiated after induction and terminated after 24 hours
 - Ketamine infusion will not be titrated

- Ketamine infusion may be terminated if the patient is having side-effects relating to the drug; Pain Service will follow the patient and assist with troubleshooting and determining the need for infusion termination
- The remainder of care will be identical to the standard therapy group

Number of Subjects

We will enroll up to 45 subjects to attain our goal of 17 subjects per group for a total of 34 accrued subjects. This is to ensure our goal is met based on the randomization list, as well as to account for any withdrawals that occur throughout the study.

Primary Study Outcome

Total cumulative perioperative opioid dose measured in morphine equivalents from induction of anesthesia until 48 hours after induction of anesthesia.

Secondary Study Outcomes

Visual analog pain scores measured from PACU arrival until 48 hours after induction of anesthesia. PONV and pruritus recorded from PACU arrival until discharge from hospital. Length of stay in hospital will be recorded. Patient satisfaction with pain management will be measured by questionnaires that patients complete at the time of discharge and at the postoperative visit with the surgeon or via telephone about 30 days after surgery.

Primary Safety Outcomes

There will be careful and continuous monitoring, intervention and recording of hemodynamics, sedation, agitation, hallucinations, delirium, and adverse respiratory events.

Standardized nursing procedures will be used including vital signs, RASS sedation scores, according to standard intensive post-surgical requirements. Standardized single dose regimen for ketamine.

Data

- **Pre-operative data**
 - Age
 - Gender
 - Height, weight, BMI
 - ASA classification
 - Medical problems
 - Surgical history
 - Home medications
 - Home CPAP?
 - Allergies

- Presence of *active* chronic pain? If so, what is it?
- Currently taking opioids on a daily basis for the past 1 month or greater? If so, quantitate daily dose in morphine equivalents (ME)
- **Post-operative data**
 - Total opioid dose in ME from OR to discharge
 - May look separately at OR, PACU, 1st 24 hours, 2nd 24 hours
 - Pain scores over course of hospitalization
 - May look separately at PACU, 1st 24 hours, 2nd 24 hours
 - PONV
 - Need for additional anti-emetics during hospitalization
 - Pruritus
 - Need for anti-histamines during hospitalization
 - Sedation
 - Average RASS scores 1st 24 hours
 - Any episodes of (-)3 or worse RASS
 - Any evidence of sedation in nursing notes
 - Agitation
 - Average RASS scores 1st 24 hours
 - Any episodes of (+) RASS scores
 - Any evidence of agitation from nursing notes
 - Hallucinations
 - Ketamine drip d/c
 - Review nursing and Pain Service notes
 - Delirium
 - Ketamine drip d/c
 - Review nursing and clinical notes
 - Adverse respiratory events
 - Rapid response events
 - Naloxone administration
 - Change in level of care (intermediate or ICU)
 - Review of nursing notes and clinician progress notes
 - Length of Stay
 - Hours
 - Use of CPAP while inpatient. Y/N
 - Patient satisfaction with pain management questionnaires
 - First questionnaire will be completed by the patient at the time of discharge from the hospital.
 - Second questionnaire will be completed by the patient at the postoperative visit with the surgeon or via phone contact with the patient on or around 30 days after surgery if there has been no postoperative visit.

Subject Selection Enrollment and Withdrawal

Inclusion Criteria

- Patients > or equal to 18 years old and < 70 years old undergoing laparoscopic gastric bypass at Mayo Clinic Arizona
- BMI > or equal to 35
- Consent obtained as per Mayo Clinic policy

Exclusion Criteria

- Intolerance to ketamine
- History of schizophrenia, schizoaffective disorder or other psychiatric diagnosis with psychotic features
- Presence of unstable cardiovascular disease. (The presence of acute coronary syndrome, unstable angina, hypertension emergency, acute TIA or stroke.)
- Presence of acute elevation of intracranial or intraocular pressure
- Presence of seizure disorder
- History of substance abuse or addiction
- Creatinine > 1.5
- End-stage liver disease
- Pregnancy
- **Patients with chronic pain and/or chronic opioid therapy:**
 - In order to more closely replicate the study patient population of interest we will not exclude this patient population
 - However, we will exclude patients taking >50 morphine equivalents (ME) per day for greater than 1 month prior to surgery

Subject Recruitment, Enrollment and Screening

Appointment calendars will be screened. Those eligible will be consented by physician or study coordinator either in POE or Surgery Clinic.

Study Procedures

- **Patient Consent**
 - Patients who appear to meet the inclusion criteria and none of the exclusion criteria will be invited to participate in this study. The study will be explained to the patient, including risks and benefits by the Study Coordinator, and one of the physicians, if available.

- Each patient who agrees to participate will be required to sign and date an informed consent document prior to any study-specific testing and procedure. A copy of the signed and dated consent will be provided to the patient.
- Method for Assigning Patients to Treatment Groups
 - If the patient meets inclusion/exclusion criteria and consents to participate in the study, the morphine equivalents will be calculated by one of the investigators.
 - The REDCap database will be completed with the inclusion/exclusion criteria and morphine equivalents. REDCap will provide the randomization group for the patient.
 - The randomization group will be conveyed to the study team by the Study Coordinator.
- Data Collection and Monitoring
 - All required data is collected during the hospitalization from the electronic medical record.
 - The floor nurses will follow the already existing ketamine guidelines for Pain Service and stopping criteria.
 - The investigators will carefully monitor the subject during hospitalization for any adverse events.
- Discharge from the Hospital
 - At the time of discharge from the hospital, the patient will complete the Patient Satisfaction with Pain Management at Discharge questionnaire.
- Postoperative Visit
 - At the postoperative visit with the surgeon, the Patient Satisfaction with Pain Management questionnaire at Post-op Visit will be completed by the patient. If no postoperative visit is scheduled, this will be done via telephone contact on or around 30 days after surgery. We will allow a window of 30-60 days in case there is difficulty reaching the patient..
- Adverse events
 - Adverse events will be captured and monitored for the first 30 days following surgery to ensure patient safety.
- Data Entry into REDCap
 - The residents will complete data entry into the REDCap database.

Time Frame

Enrollment will be completed within 48 months.

Statistical Plan

Sample Size and Power Calculation

Our primary hypothesis is to check if the new management will keep patient to get less "48 hours morphine equivalent (mg)". A sample size of 17 in each group will have 80% power to detect a probability of 0.746 that an observation in new management group is less than an observation in control group using a Wilcoxon (Mann-Whitney) rank-sum test with a 0.050 one-sided significance level. In other words, we will arrange the total doses at 48 hours of patients from smallest to biggest. If 13 or more out of first 17 comes from the new management group, we will claim a success.

Statistical Methods

Basic patient characteristics, using mean \pm SD or median (range) for continuous variable and frequency (% percentage) for categorical data, will be summarized in a table. 2- group t-test, Wilcoxon rank sum test, Pearson Chi-square test or Fisher exact test will be used to compare the two kinds of management when appropriate. The "48 hours morphine equivalent (mg)" will be compared between the two groups using Wilcoxon Rank sum test. A p-value less than 0.05 will be treated as statistical significant. All statistical analyses will be performed by SAS version 9.4 software (SAS institute Inc, Cary NC).

Adverse Event Reporting Period

For this study, the follow-up period is defined as 30 days following surgery.

Medical Monitoring

It is the responsibility of the Principal Investigator to oversee the safety of the study. This safety monitoring will include careful assessment and appropriate reporting of adverse events. Medical monitoring will include a regular assessment of the number and type of serious adverse events

Data Security and Confidentiality

All electronic data will be stored in a password-protected database (RedCap). The data storage will be restricted to facility computers that are password protected. Relevant clinical information will be reported only with collective data with no identities revealed.

Study Monitoring Plan

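### Pain scores are compared without any baseline pain covariate although chronic-pain patients are deliberately eligible: the comparison is valid, but gives up precision at 17 per arm

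*Combined protocol and SAP*

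**What the plan says.** **Who is eligible.** On chronic pain and chronic opioid therapy, Exclusion Criteria states: "In order to more closely replicate the study patient population of interest we will not exclude this patient population". The only limit is on opioid dose: "we will exclude patients taking >50 morphine equivalents (ME) per day for greater than 1 month prior to surgery". It does not limit pain.

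**What pain is used for.** The hypothesis closing the Background is that ketamine "provides superior pain control and decreases post-operative opioid use versus standard non-ketamine therapy". The Secondary Objective covers the effect of "intravenous ketamine on perioperative pain scores, patient satisfaction with pain management, and length of stay in hospital". Secondary Study Outcomes defines the measure as "Visual analog pain scores measured from PACU arrival until 48 hours after induction of anesthesia".

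**What is recorded beforehand.** The pre-operative list under Data has "Presence of *active* chronic pain? If so, what is it" and a question on daily opioid use with the instruction "If so, quantitate daily dose in morphine equivalents (ME". Pain scores are listed only among the post-operative items ("Pain scores over course of hospitalization").

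**How baseline data are used.** Under Study Procedures, eligibility and morphine equivalents are entered in REDCap before the group is released; no stratification factor is named. Statistical Methods has a descriptive table of patient characteristics and four two-group tests (t, Wilcoxon, chi-square, Fisher). It mentions no covariate, stratum or subgroup.

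**The concern.** The population is mixed with respect to pain before surgery, by choice. The form asks about chronic pain, so it was evidently thought relevant, yet the answer has no stated role in allocation or in the between-arm comparison. The first pain score is taken at PACU arrival. In the ketamine arm the bolus is given with induction and the infusion starts after it, so that score cannot serve as a baseline.

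If pain before surgery predicts pain afterwards, two things follow at 17 per arm. Between-patient variation that could be removed stays in the comparison and lowers its power. An uneven split of chronic-pain patients can also move the observed difference in either direction, with no planned analysis to account for it. What is at stake is the precision of one secondary outcome, although that outcome carries the pain-control part of the stated hypothesis.

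**Working it through.** **1. The plan's own figure.** The only sample size calculation is for 48-hour morphine equivalents: Wilcoxon test, one-sided 0.05, 80% power, P = 0.746. By Noether's formula, N = (1.645 + 0.842)² / [3 × (0.746 − 0.5)²] = 34.05, or 17.03 per arm; power at 17 per arm is 79.9%. The stated 17 reproduces, but it concerns opioid dose. No figure is given for pain.

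**2. Is the unadjusted comparison valid?** A simulation with no treatment effect, 30% chronic-pain prevalence, a 2-point higher score in those patients and residual SD 2 (all assumed) gave a type I error of 5.0% and a mean difference of −0.001. There is no bias.

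**3. Chance imbalance.** Take the number of chronic-pain patients in each arm as Binomial(17, prevalence).

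| Assumed prevalence | Chance the arms differ by 4 or more |
|---|---|
| 10% | 4% |
| 20% | 13% |
| 30% | 19% |
| 40% | 22% |
| 50% | 23% |

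A 4-patient difference moves the difference in means by 4 × shift / 17: 0.24 points for a 1-point shift and 0.47 for a 2-point shift. With 30% prevalence, a 2-point shift and residual SD 2, the total SD is √(4 + 4 × 0.3 × 0.7) = 2.2, so 0.47 points is about 0.21 SD.

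**4. Precision from a pre-operative score.** Adjustment for a covariate with correlation r to the outcome leaves a fraction 1 − r² of the variance. Assume a 0.8 SD difference, 17 per arm and two-sided 0.05. Then power = Φ(0.8 / √[(2/17)(1 − r²)] − 1.96). Unadjusted: 0.8 / 0.343 = 2.332, and Φ(0.372) = 64.5%.

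| r | Variance left | Power |
|---|---|---|
| 0 (unadjusted) | 1.00 | 64.5% |
| 0.1 | 0.99 | 65.0% |
| 0.2 | 0.96 | 66.3% |
| 0.3 | 0.91 | 68.6% |
| 0.5 | 0.75 | 76.8% |
| 0.6 | 0.64 | 83.0% |

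With the noncentral t distribution the levels are lower (62% unadjusted; 66%, 74% and 81% at r = 0.3, 0.5 and 0.6), but the gains are similar.

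**5. Precision from the yes/no item alone.** With residual variance 4, the share explained is v / (4 + v), where v = shift² × prevalence × (1 − prevalence).

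| Shift | Prevalence | v | Share removed | Power |
|---|---|---|---|---|
| 1 point | 10% | 0.09 | 2.2% | 65.5% |
| 1 point | 30% | 0.21 | 5.0% | 66.7% |
| 2 points | 10% | 0.36 | 8.3% | 68.3% |
| 2 points | 30% | 0.84 | 17.4% | 72.8% |

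**6. Where the gain disappears.** Steps 4 and 5 ignore the cost of estimating the covariate's slope. For a normally distributed covariate this inflates the variance on average by 1 + 1/(34 − 4) = 1.033. Adjustment then breaks even at 1 − r² = 1/1.033, that is r² = 0.032, or r of about 0.18. The small gains shown at r = 0.1 and for the weakest yes/no case are therefore nominal.

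**The case against.** The strongest reply is that randomization already deals with this. A reader might infer that the pain comparison is confounded because pre-existing pain is mixed with surgical pain. The documents do not support that: allocation is random, so pre-existing pain is balanced in expectation, and step 2 shows the test keeps its level. Adjustment is a matter of efficiency, and the plan contains no contradiction here. This stands.

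A second reply is that pre-existing pain may not carry over strongly into post-operative scores. Both arms have hydromorphone PCA with scheduled acetaminophen and ketorolac, so some of it may appear as opioid use instead of higher scores. Many patients without chronic pain may also score near zero before surgery. Either could make the correlation low. This stands too, and is why low correlations are in the table.

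Third, pain is one of several secondary outcomes and has no power claim. That is correct and limits the importance of the point.

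Fourth, a reader might infer that the chronic-pain item is not used at all. That goes too far: it could appear in the baseline table and reveal an imbalance there. What the plan lacks is any role for it in the comparison. Recorded opioid dose does not fill the gap. It is a separate item, it does not measure pain intensity, and the text does not say that it stratifies allocation.

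**Conclusion.** The point holds as a low-priority improvement in efficiency. The plan collects a baseline item on chronic pain and omits it from the pain comparison, and it lists no pre-operative score that could do better. The unadjusted comparison is valid; it gives up some precision and leaves chance imbalance unaddressed.

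Under the assumed 0.8 SD effect, the gain runs from essentially nothing at a correlation of 0.1 to about 18 percentage points of power at 0.6 (64.5% to 83.0%). The yes/no item alone gains from about 1 to 8 points. The effect size, correlation, prevalence, point shift and residual SD are all assumptions; the documents supply only the 17 per arm. Nothing here bears on the primary opioid analysis or its sample size.

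**What to change.** In Statistical Methods, add that one summary of each patient's visual analog scores from PACU arrival to 48 hours after induction, for example the mean, is compared between arms by ANCOVA adjusted for the active-chronic-pain yes/no item. The summary has to be named first: the plan defines none and says only that periods may be looked at separately.

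For patients not yet treated, also record one visual analog score before any study drug and use it as the covariate. The documents do not state enrollment status, and this is version 4 of the protocol. Patients already treated would lack the score. In that case keep the yes/no item for the main analysis of all patients and report the score-adjusted analysis in those who have it as supportive. The choice should be fixed before outcome data are examined by arm.

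The cost is one extra field before surgery, a sentence or two of text and one degree of freedom. The gain may be small if the correlation is low.

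### Hallucinations are a primary safety outcome, but no structured patient question about them is specified in either arm, and the listed sources can search the two arms unequally

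*Combined protocol and SAP*

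**What the plan says.** The Secondary Objective makes the presence of hallucinations part of the safety and tolerability assessment. Primary Safety Outcomes promises: "There will be careful and continuous monitoring, intervention and recording of hemodynamics, sedation, agitation, hallucinations, delirium, and adverse respiratory events".

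The measurement is set out in the Data section, under Post-operative data. Hallucinations have two entries: "Ketamine drip d/c" and "Review nursing and Pain Service notes". Delirium has the drip entry and a review of nursing and clinical notes. Study Procedures (Data Collection and Monitoring) adds: "All required data is collected during the hospitalization from the electronic medical record".

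The one bedside scale named for these outcomes is RASS ("Standardized nursing procedures will be used including vital signs, RASS sedation scores, according to standard intensive post-surgical requirements"), and the Data section uses it for sedation and agitation only. Hallucinations have no definition, scale, scheduled question or assessment time.

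The Pain Service's role appears in the ketamine-arm description, within the item on stopping the infusion: "Pain Service will follow the patient and assist with troubleshooting and determining the need for infusion termination". The comparator is standard therapy. No placebo or blinding is described, and the allocated group is passed to the study team.

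All patients are asked directly about one subjective matter at discharge, where "the patient will complete the Patient Satisfaction with Pain Management at Discharge questionnaire". The items of that form are not shown.

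**The concern.** A hallucination is known first to the patient. It reaches the study record only if the patient mentions it or staff notice it, and someone then writes it down. Under the listed sources, a patient whose event fails at either step is counted as having had none.

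The sources also differ between arms. A ketamine drip cannot be discontinued in a patient who never had one. Pain Service notes may be plentiful in one arm and sparse in the other. Staff who know the allocation may ask ketamine patients more closely, or may chart the same remark differently.

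At stake is the tolerability statement in the Secondary Objective. With 17 patients per arm it will rest on a handful of recorded events or none, and the reader could not tell whether a small count reflects the drug or the charting.

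**Working it through.** **Inputs from the protocol.** 17 patients per group (Number of Subjects; Sample Size and Power Calculation).

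**Assumed inputs.** The documents give no hallucination rate and no capture rate. Let p be the true risk of at least one hallucination on ketamine (10% to 30%). Let s be the proportion of affected patients whose event is recorded (20% to 100%).

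**The plan's own figure.** The group size was set for the opioid endpoint, and it reproduces. By Noether's formula, N = (1.645 + 0.842)² / (12 × 0.25 × (0.746 − 0.5)²) = 34.05, or 17.03 per arm. The protocol makes no calculation for hallucinations.

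**Step 1: chance that the ketamine arm shows no event.** Expected recorded events = 17 × p × s. P(zero recorded) = (1 − p × s)^17. For p = 20% and s = 50%, the expected count is 17 × 0.20 × 0.50 = 1.7 of 3.4 true cases, and P(zero) = 0.90^17 = 0.167.

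| True risk | s = 20% | s = 50% | s = 75% | s = 90% | s = 100% |
|---|---|---|---|---|---|
| 10% | 0.71 | 0.42 | 0.27 | 0.20 | 0.17 |
| 20% | 0.50 | 0.17 | 0.06 | 0.03 | 0.02 |
| 30% | 0.35 | 0.06 | 0.01 | 0.005 | 0.002 |

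**Step 2: direction of bias between arms.** Expected recorded difference = p(ketamine) × s(ketamine) − p(control) × s(control).

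- Equal capture of 50%, true risks 20% and 0%: 0.20 × 0.50 − 0 = 10 percentage points, against a true 20. The difference is understated.
- Unequal capture of 75% on ketamine and 25% on control, true risk 10% in both: 0.075 − 0.025 = 5 points, against a true 0. The difference is overstated, although both arms are under-counted.

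Both patterns are compatible with the sources listed.

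**Step 3: what the sample can show in any case.** Fisher's exact test (two-sided 0.05) needs at least 5 versus 0 of 17 (p = 0.044); 4 versus 0 gives p = 0.103. At true risks of 30% and 0%, power is 0.61 with full capture, 0.33 at 75% and 0.10 at 50%. Even with full capture, 0 of 17 leaves a one-sided 95% upper bound of 1 − 0.05^(1/17) = 16.2%.

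**The case against.** **Other surveillance exists.** A reader might infer that hallucinations are found only by reading notes and that no patient is ever asked. The documents do not support that. Drip discontinuation is a second listed source, investigators monitor for adverse events in hospital, and adverse events are captured for 30 days. Nurses follow existing ketamine guidelines that are not reproduced, and the questionnaire items are not shown; either might contain a suitable question. This limits the point to what the plan specifies. It does not remove it: the adverse-event provisions state no method of asking. Drip discontinuation occurs in one arm only, needs someone to have recognised a problem first, and as listed carries no reason for stopping.

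**The error need not favour ketamine.** A reader might infer that poor charting will make the drug look tolerable. Closer attention to ketamine patients could equally exaggerate the contrast, as step 2 shows.

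**Nausea, vomiting and pruritus.** A reader might extend the point to these because drug use is listed beside each. Secondary Study Outcomes says both are recorded from PACU arrival until discharge, so the extension is not made here.

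**Sample size limits the conclusion too.** This stands. If capture is already 75% and the true risk 20%, raising capture to 90% only moves the chance of a zero from 0.06 to 0.03. No tolerability decision rule exists for a missed event to overturn.

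**The remedy is imperfect.** A single question at discharge relies on memory and on patients who may know their treatment. That is why it should stand beside the chart count and not replace it.

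**Conclusion.** The point holds in this form: for a primary safety outcome, the plan specifies no structured patient question in either arm, and its listed sources can both miss events and look harder in one arm. Under-counting and unequal searching can occur together, so the direction of bias in the between-arm difference is unknown.

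The size rests on assumed capture. At 20% true risk, a recorded zero has probability about 0.50, 0.17, 0.06 and 0.03 at 20%, 50%, 75% and 90% capture. The qualitative result holds from 10% to 30% risk: the lower the capture, the less a zero says about the drug.

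The primary opioid outcome is not affected. Delirium shares the weakness, since it too rests on drip discontinuation and notes.

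**What to change.** 1. Add to the discharge questionnaire one yes/no item, for example: *Since your surgery, did you see, hear or feel things that were not there?* Ask about vivid or disturbing dreams in a separate yes/no item, so that a positive answer to the first still measures the listed outcome. If the form already asks this, say so in the Data section.
2. Report patient-reported hallucinations by arm beside the chart-documented count, with the number of patients who answered.
3. Report drip discontinuation on its own for the ketamine arm, not as a hallucination measure compared between arms.
4. Label note-based hallucinations and delirium as clinician-documented, so that they are not read as incidence.

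**Cost.** A minor amendment, two yes/no items and the matching REDCap fields, with no extra visit or procedure. Answers come from one recall by unblinded patients, and the event rate will probably be higher than from notes. Anyone discharged before the change will have no patient-reported value; the protocol is at its fourth version and does not say how many patients that would be.
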